#### **10.1.6.5. Data Collection and Management Responsibilities**

Data collection is the responsibility of the clinical study staff under the supervision of the Investigator. During the study, the Investigator will maintain complete and accurate documentation for the study.

All eCRF data will be entered into a validated database compliant with 21 CFR Part 11. Laboratory data will be either manually entered or imported to the clinical database electronically. All data entry, verification, and validation will be performed in accordance with the current SOPs of the Sponsor or its designee. The database will be authorized for lock once no data queries are outstanding, all study data are considered clean, and all defined procedures are completed.

The Clinical Site will be provided with eCRFs and ePRO/eCOA devices in which to record all the protocol-specified data for each Participant. Entries made in the eCRF must be verifiable against source documents, or in certain circumstances as directed by the Sponsor, entries will have been directly entered into the eCRF; in such cases, the entry in the eCRF will be considered as the source data. Data reported in the eCRF that are derived from source documents should be consistent with the source documents or the discrepancies should be explained. The Investigator will be responsible for reviewing all data and eCRF entries and will sign and date the designated pages in each Participant's eCRF, verifying that the information is true and correct. Queries generated by Data Management will be sent to the Clinical Site for resolution. The Investigator is responsible for the review and approval of all responses to eCRF queries.

#### **10.1.6.6. Protocol Deviations**

The Investigator will not deviate from this protocol for any reason without prior written approval by the Medical Monitor on behalf of the Sponsor except in the case of a medical emergency when the change is necessary to eliminate an apparent and immediate hazard to the Participant. In the event of such an emergency, the Investigator will notify the Medical Monitor immediately by phone, notify the IRB, and confirm with the Medical Monitor in writing within 5 working days of the change being implemented.

Protocol deviations will be tracked through the EDC.

#### **10.1.6.7. Source Documents**

As defined in the ICH Guidelines for Good Clinical Practice E6(R2), Section 1.52, source documents may include: original documents, data, and records (e.g., hospital records, clinical and office charts, laboratory notes, memoranda, Participant's diaries or evaluation checklists, pharmacy dispensing records, recorded data from automated instruments, copies or transcriptions certified after verification as being accurate and complete, microfiches, photographic negatives, microfilm or magnetic media, x rays, Participant files, and records kept at the pharmacy, at the laboratories, and at medico-technical departments involved in the clinical study).

Source documents provide evidence for the existence of the Participant and substantiate the integrity of the data collected. Source documents are filed at the Investigator's Site.

The Investigator may need to request previous medical records or transfer records, depending on the study. Current medical records must also be available.

#### **10.1.7. Data Management**

All Participant data will be entered into a password-protected validated EDC system by authorized Site personnel according to the CRO's SOPs.

Data discrepancies identified via programmed edit checks, manual data review or discovered during data monitoring will be addressed and resolved. An audit trail in the EDC system will list all changes made to the data, with a date/time stamp and user initials. Upon database lock, occurring after data are declared clean and eCRFs have been approved by the Investigator, the CRO will provide SAS datasets to the Sponsor and designated Statistician for data analysis via secure data transfer specified in the Study Data Management Plan.

#### **10.1.8. Recordkeeping and Retention**

Data generated for the study should be stored in a limited-access file area and be accessible only to representatives of the Clinical Site, the Sponsor and its representatives, and FDA/relevant health authorities/regulatory agencies. All reports and communications relating to Participants will identify Participants only by Participant identification number. Complete Participant identification will be kept by the Investigator. This information will be treated with strict adherence to professional standards of confidentiality.

The Investigator must in reasonable time, upon request from any properly authorized officer or employee of the FDA/relevant health authority/regulatory agency, permit such officer or employee to have access to requested records and reports, and copy and verify any records or reports made by the Investigator. Upon notification of a visit by the FDA/relevant health authority/regulatory agency, the Investigator will contact the Sponsor immediately. The Investigator will also grant the Sponsor's representatives the same privileges offered to FDA/relevant health authority or regulatory agents/officers/employees.

The Investigator must provide the Sponsor or its designee with the following documents prior to study initiation and retain a copy in the study file:

- A completed and signed Form FDA 1572. If, during the study, any changes occur that are not reflected on the current 1572, a new 1572 must be completed and returned to the Sponsor or its designee for submission to the FDA
- Current signed curricula vitae (within 2 years prior to study initiation) and current medical licenses for the Investigator and all co-Investigators listed on the 1572
- A copy of the original approval by the IRB for conducting the study. Renewals, with continuance of the study, must be submitted at yearly intervals or as required by IRB policy.
- A copy of the IRB-approved ICF
- The IRB member list and/or DHHS General Assurance Number (if the IRB has an Assurance number)
- A copy of the original approval by the IBC for conducting the study, if applicable. Renewals, with continuance of the study, must be submitted at yearly intervals or as required by IBC policy.
- Signed Financial Disclosure Forms for all personnel listed on the 1572 with a statement of non-voting by study staff
- The signature page of this protocol signed and dated by the Investigator
- The signature page of the IB signed and dated by the Investigator

In addition to the documents listed above, the Clinical Site will also retain the following items:

- Certifications and laboratory reference ranges for all local laboratories used for this study
- A copy of delegation of authority log
- All original ICFs with required signatures
- All IRB correspondence (e.g., informed consent [including any approved revisions], protocol, AE, advertisements, newsletters)
- All IBC correspondence
- A copy of the Study Monitoring Log
- Clinical and nonclinical supply shipment forms
- Copies of all pertinent correspondence pertaining to the study (except budget issues) between the Sponsor and the Site
- Copies of all SAE reports submitted to the Sponsor
- Copies of all Investigator Safety Reports submitted to the Site by the Sponsor
- Copies of approved package labelling, if applicable

### **10.1.9. Study and Site Start and Closure**

The study may be temporarily suspended or prematurely terminated if there is sufficient reasonable cause. Written notification documenting the reason for study suspension or termination will be provided by the Sponsor to Investigators and regulatory authorities. If the study is prematurely terminated or suspended, the Investigator will promptly inform Participants and the IRB and will provide the reasons for the termination or suspension. Participants will be contacted, as applicable, and be informed of changes to Study Visit schedules.

The Sponsor reserves the right to discontinue the study for any safety, ethical, or administrative reason at any time.

The Sponsor or designee reserves the right to close a Clinical Site or terminate the study at any time for any reason at the sole discretion of the Sponsor. Study sites will be closed upon study completion.

The Investigator may initiate Clinical Site closure at any time, provided reasonable cause and sufficient notice is given in advance of the intended termination.

Reasons for the early closure of a Clinical Site by the Sponsor or Investigator may include but are not limited to:

- Failure of the Investigator to comply with the protocol, the requirements of the IRB/IEC or local health authorities, the Sponsor's procedures, or GCP guidelines
- Inadequate recruitment of Participants by the Investigator
- Discontinuation of further study drug development

If the study is prematurely terminated or suspended, the Sponsor will promptly inform the Investigators, IRBs, the regulatory authorities, and any CROs used in the study of the reason for termination or suspension, as specified by the applicable regulatory requirements. The Investigator will promptly inform the Participants and should ensure appropriate Participant therapy and/or follow-up.

### **10.1.10. Publication Policy**

The study will be conducted in accordance with the publication and data sharing policies and regulations as defined in the agreement between the Sponsor and the institution. In addition, this study will be registered at [www.ClinicalTrials.gov](http://www.ClinicalTrials.gov) and in any other protocol registries required by the regions in which the study is conducted, and the results from this study will become publicly available.

None of the data resulting from this study will be allowed to be presented or published in any form, by the Investigator or any other person, without the prior written approval of the Sponsor.

### **10.1.11. Insurance**

Matters relating to insurance for this study are to be defined in the agreement between the Sponsor and the institution.

## 10.2. Appendix 2. Adverse Events: Definitions and Procedures for Recording, Evaluating, Follow-up, and Reporting

### 10.2.1. Definition of AE

AE Definition

 
• An AE/TEAE is any untoward medical occurrence associated with the use of an investigational product or study procedure in a clinical study Participant whether or not considered related to the study intervention.
 
• NOTE: An AE/TEAE can therefore be any unfavorable and unintended sign (including an abnormal laboratory finding), symptom, or disease (new or exacerbated) temporally associated with the use of study intervention or procedure.
 

Events Meeting the AE Definition

 
• Any abnormal laboratory test results (hematology, or clinical chemistry) or other safety assessments (e.g., ECG, radiological scans, vital signs measurements), including those that worsen from baseline, considered clinically significant in the medical and scientific judgment of the investigator (i.e., not related to progression of underlying disease).
 
• Exacerbation of a chronic or intermittent pre-existing condition including either an increase in frequency and/or intensity of the condition.
 
• New conditions detected or diagnosed after study intervention administration even though it may have been present before the start of the study.
 
• Signs, symptoms, or the clinical sequelae of a suspected drug-drug interaction.
 
• Signs, symptoms, or the clinical sequelae of a suspected overdose of either study intervention or a concomitant medication. Overdose per se will not be reported as an AE/SAE unless it is an intentional overdose taken with possible suicidal/self-harming intent. Such overdoses should be reported regardless of sequelae.
 

Events NOT Meeting the AE Definition

 
• Any clinically significant abnormal laboratory findings or other abnormal safety assessments that are associated with the underlying disease, unless judged by the Investigator to be more severe than expected for the Participant's condition.
 
• The disease/disorder being studied or expected progression, signs, or symptoms of the disease/disorder being studied, unless more severe than expected for the Participant's condition.
 
• Medical or surgical procedure (e.g., endoscopy, appendectomy): the condition that
 

leads to the procedure is the AE.

- Situations in which an untoward medical occurrence did not occur (social and/or convenience admission to a hospital).
- Anticipated day-to-day fluctuations of pre-existing disease(s) or condition(s) present or detected at the start of the study that do not worsen.

### 10.2.2. Definition of TEAE

Treatment-Emergent Adverse Event is defined as:

- An event that emerges during treatment, having been absent at pretreatment, or worsens relative to the pretreatment state, as defined in the E9 Guidance.
- The TEAE is not related to causality / drug relatedness. It may or may not be related to the drug but is considered a TEAE due to its appearance at or after the treatment has been administered.

### 10.2.3. Definition of SAE/TEAE

If an event is not an AE per the definition above, then it cannot be an SAE even if serious conditions are met (e.g., hospitalization for signs/symptoms of the disease under study, death due to progression of disease).

An SAE is defined as any untoward medical occurrence that, at any dose:

a. Results in death

b. Is life-threatening

The term “life-threatening” in the definition of “serious” refers to an event in which the Participant was at risk of death at the time of the event. It does not refer to an event, which hypothetically might have caused death, if it were more severe.

c. Requires inpatient hospitalization or prolongation of existing hospitalization

- In general, hospitalization signifies that the Participant has been detained (usually involving at least an overnight stay) at the hospital or emergency ward for observation and/or treatment that would not have been appropriate in the physician’s office or outpatient setting. Complications that occur during hospitalization are AEs. If a complication prolongs hospitalization or fulfills any other serious criteria, the event is serious. When in doubt as to whether “hospitalization” occurred or was necessary, the AE should be considered serious.
- Hospitalization for elective treatment of a pre-existing condition that did not worsen from baseline is not considered an AE.

d. Results in persistent disability/incapacity

 
• The term “disability” means a substantial disruption of a person’s ability to conduct normal life functions.
 
• This definition is not intended to include experiences of relatively minor medical significance such as uncomplicated headache, nausea, vomiting, diarrhea, influenza, and accidental trauma (e.g., sprained ankle), which may interfere with or prevent everyday life functions but do not constitute a substantial disruption.
 

e. Is a congenital anomaly/birth defect
f. Other situations:

 
• Medical or scientific judgment should be exercised in deciding whether SAE reporting is appropriate in other situations such as important medical events that may not be immediately life-threatening or result in death or hospitalization but may jeopardize the Participant or may require medical or surgical intervention to prevent one of the other outcomes listed in the above definition. These events should usually be considered serious.
 
• Examples of such events include invasive or malignant cancers; intensive treatment in an emergency room or at home for allergic bronchospasm, blood dyscrasias, or convulsions that do not result in hospitalization; or development of drug dependency or drug abuse.
 

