### **2.2.3. Unmet Clinical Need**

Diabetic peripheral neuropathy is a serious complication of diabetes mellitus (DM), with painful DPN being a frequent manifestation of neuropathy. Tight glycemic control and treatment of cardiovascular risk factors are effective preventive measures, but DPN remains the most common complication of DM, affecting 60% to 70% of diabetics. Progressive DPN may result in loss of function in affected legs, infection, and amputation.

Current treatments provide symptomatic relief of the pain associated with DPN. A clear unmet medical need exists for treatments that address the underlying pathology of DPN and prevent the progressive destruction and loss of function associated with this disease.

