#### Infections and infestations; Skin and Subcutaneous disorders

Because patients with diabetic peripheral neuropathy are at an increased risk to develop skin lesions (e.g., blisters, ulcers) and various lower limb infectious complications (e.g., cellulitis, osteomyelitis) that may be associated with systemic infections (e.g., bacteremia, sepsis, or septic shock), all of these types of medical problems that occur after Randomization (Day 0) will be considered AESIs. In addition, any amputations involving the lower extremity, development of Charcot foot, or other similar complications will also be considered AESIs.

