#### **8.5.8. Disease-Related Events and/or Disease-Related Outcomes Not Qualifying as AEs or SAEs**

Except for signs and symptoms of diabetic peripheral neuropathy (i.e., numbness, pain, tingling or burning sensation, cramps, and increased sensitivity to touch), all disease-related events or disease-related outcomes qualify as AEs or SAEs.

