### **10.1.5. Committee Structure**

#### **10.1.5.1. Data Safety Monitoring Board**

An independent Data Safety Monitoring Board (DSMB) has been chartered for this study to review all safety data during the study and safeguard the interests of the Participants. The objectives of the DSMB meetings are to review the safety outcomes of the study and provide guidance to the Sponsor regarding the safety of Engensis. The DSMB will meet periodically and review a limited set of unblinded tables and/or listings, including all reported AEs/TEAEs, SAEs/TEAEs, and AESIs. The data analyses for the DSMB meetings will be directly provided to the DSMB members; no data will be released to the Sponsor and blinded designees. No adjustment will be made for multiple testing due to the DSMB data review.

The DSMB will consist of two physicians with expertise in clinical studies and one statistician. Members of the DSMB will be independent of study conduct and free of conflict of interest, or measures should be in place to minimize perceived conflicts of interest. An independent biostatistician will be available for consultation.

The DSMB will operate under the rules of the charter, which have been reviewed at organizational meetings of the DSMB. Each data element that the DSMB requires to assess the safety of Engensis will be agreed upon prior to study start. Routine DSMB meetings will be regularly scheduled per the DSMB Chair to review safety and 12-week pooled all-cause mortality data, including unblinded Participant narratives. The DSMB Chair may request additional unblinded information at any time to further understand a safety trend. Ad hoc DSMB meetings can be convened at any time at the discretion of the DSMB Chair or the Sponsor. However, the DSMB Chair may not share any unblinded information with the Sponsor unless it is deemed necessary for the Sponsor to address a potential safety concern. The DSMB will provide recommendations to the Sponsor in accordance with the DSMB Charter.

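### Protocol Section 10.2.3 names death from disease progression as an event that cannot be an SAE, which conflicts with Section 8.5.8 and leaves such a death with no described reporting route

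*Protocol*

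**What the plan says.** Protocol Section 10.2.3 opens with a condition: "If an event is not an AE per the definition above, then it cannot be an SAE even if serious conditions are met". It illustrates that condition with two cases: "even if serious conditions are met (e.g., hospitalization for signs/symptoms of the disease under study, death due to progression of disease". The list of seriousness criteria that follows in the same section begins with "Results in death".

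The AE definition that the condition points back to is in Section 10.2.1. It leaves out the expected course of the disease being studied, but brings a case back in when it is worse than anticipated for that participant. It also counts as AEs any exacerbation of a pre-existing condition and any condition newly detected after dosing.

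Section 8.5.8 exempts a short list of DPN signs and symptoms (numbness, pain, tingling or burning, cramps, sensitivity to touch). Beyond that list, "all disease-related events or disease-related outcomes qualify as AEs or SAEs".

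The Definitions at the front of the SAP exclude changes consistent with natural disease progression from AEs, with no exception for severity.

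The causality part of Section 10.2.4 says that death and hospitalization are criteria for seriousness and are not to be entered as the SAE itself. The 24-hour duty in Sections 8.5.1 and 8.5.3 and in note 28 to the Schedule of Activities is written for SAEs. Under Section 10.1.5.1, routine DSMB meetings "review safety and 12-week pooled all-cause mortality data".

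**The concern.** A site with a death that it judges to be due to the disease has been given incompatible instructions. If it follows the example in 10.2.3, the death is not an SAE. If it follows 8.5.8, or the first seriousness criterion, it is.

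Which rule the site picks decides whether the death is reported within 24 hours and whether it counts towards TESAE incidence, a secondary safety endpoint in Section 3. It may also decide whether the DSMB sees the death at all. In a placebo-controlled trial of a product whose angiogenic potential is listed as a risk (Section 2.3.1), the count of deaths by arm should not rest on a site's opinion about cause.

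**Working it through.** There is no figure in the plan to reproduce. The check is a comparison of texts.

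**Step 1. How each rule classifies a death attributed to disease progression**

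| Source | Rule | Result |
|---|---|---|
| Protocol 10.2.1 | Expected course is not an AE, unless worse than anticipated | Depends on the investigator's judgement |
| Protocol 10.2.3, opening | Not an AE, so not an SAE; death from progression is a named example | Not an SAE |
| Protocol 10.2.3, criterion (a) | An untoward occurrence that is fatal is serious | SAE |
| Protocol 8.5.8 | Only the listed DPN signs and symptoms are exempt | AE or SAE |
| SAP Definitions, AE | Natural progression excluded, no severity exception | Not an AE |
| SAP Definitions, serious AE | An untoward occurrence resulting in death is serious | SAE |

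Death is a disease-related outcome and is not on the exempt list in 8.5.8. The second and fourth rows therefore cannot both be followed. The first and fifth rows also differ: a fatal course worse than anticipated is an AE under the protocol but has no way back in under the SAP's AE wording.

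**Step 2. Does the opening condition in 10.2.3 resolve it?** Only in part. A death would usually count as worse than anticipated for a participant with painful DPN, so 10.2.1 alone would normally make the underlying event an AE. But the sentence goes on to name death from progression as a case that falls outside the definition. It tells the site how to classify the event that 10.2.1 would have captured.

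**Step 3. Can the death be recorded some other way?** Section 10.2.4 requires an underlying event to carry the death. If that event is classed as progression and not as an AE, nothing carries it. Looking for another route in the supplied text:

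- Section 7.2 lists six discontinuation reasons, none of which is death. The nearest are adverse event and other.
- The Schedule of Activities has no vital-status item.
- The DSMB inputs named in the Synopsis and in 10.1.5.1 are reported AEs, TEAEs, SAEs and AESIs.
- SAP Section 8.2 (disposition) and Section 8.5.3 (adverse events) list no summary of deaths.

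**Step 4. How large is the exposed set?** The documents give no rate of death or of events attributed to progression, so no expected count can be derived. Section 8.5.4.2 names limb infection, sepsis, amputation and Charcot foot as AESIs, and 10.2.1 makes new conditions and exacerbations AEs. What remains is a death that a site attributes to the expected course of the disease within 180 days, which is probably rare.

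For scale only: at N = 152 each arm has 152/2 = 76 participants, so one omitted death is 1/76 = 1.3% of an arm. At N = 250 each arm has 250/2 = 125, and one death is 1/125 = 0.8%.

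**The case against.** The strongest reply is that 10.2.3 creates no exclusion of its own. It applies only to an event that already fails the AE definition, and 10.2.1 is generous about what counts. That is right, and it narrows the point. It does not remove it, because the named example points the site the wrong way.

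Four stronger readings are tempting, and the documents do not support them.

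- *Hospitalizations also go unreported.* A reader might infer that the hospitalization example contradicts 8.5.8 too. It largely does not. It concerns signs and symptoms of the disease under study, and 8.5.8 exempts DPN signs and symptoms as well.
- *A fatal foot infection or sepsis is never an SAE.* A reader might infer this from Section 2.2.3, which says "Progressive DPN may result in loss of function in affected legs, infection, and amputation". That is background on unmet need and not a classification rule. A new infection is an AE under 10.2.1, and Section 8.5.4.2 makes AESIs of "various lower limb infectious complications (e.g., cellulitis, osteomyelitis) that may be associated with systemic infections". The DSMB reviews AESIs, and the SAP tabulates them. AESI status does not by itself trigger the 24-hour rule, so it is only a partial safeguard.
- *The DSMB's mortality review is contradicted.* Counting all deaths does not require each one to be an SAE. What is missing is a described route for capturing them.
- *A particular share of participants is affected.* Nothing in the documents supports any rate.

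It is also fair to say that the CRFs and the DSMB Charter are not among the documents and may capture deaths, and that the list in Section 7.2 is not worded as exhaustive.

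**Conclusion.** The point holds for deaths. The death example in 10.2.3 conflicts with 8.5.8, sits badly with criterion (a) in its own section, and is not reconciled with 10.2.1 or with the SAP's AE definition. Read with 10.2.4, it allows a death attributed to progression to miss 24-hour reporting and the TESAE table. The supplied text shows no other path by which that death would reach the all-cause mortality review.

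The number of such deaths cannot be estimated from the documents and is probably small. The conclusion assumes that some site will rely on the example as written, and that no document outside those supplied already requires every death to be recorded. It does not extend to a claim that deaths and admissions in general escape reporting. The point is worth correcting because the wording bears on a secondary safety endpoint and on mortality oversight, and because the correction is cheap.

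**What to change.** - **Protocol 10.2.3:** delete the example of death due to progression. State that any event with a fatal outcome from first injection to Day 180 is recorded and reported as an SAE whatever its cause.
- **Protocol 10.2.1 and 8.5.8, and the SAP's AE definition:** reconcile them so that one rule covers disease progression, including whether a course worse than anticipated counts as an AE.
- **Protocol 7.2:** add death to the discontinuation reasons.
- **SAP:** add a summary of all-cause deaths by arm.

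Leave the exemption for DPN signs and symptoms as it stands. It is deliberate, and the hospitalization example largely agrees with it, so there is no case here for making nearly every admission an SAE.

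The cost is wording in the protocol and SAP and possibly a few more SAE reports. Sample size and the efficacy analyses are not affected.
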